***c) Part III: Mother's Perceived Barriers Regarding Kangaroo Care***

In Part III, the mothers' perceived barrier subscales questionnaire was used, adapted from the original KCQ tool developed by Arthur J. Angler & Eileen Brumbaugh, Ludington-Hoe et al. (2013) with slight modifications made to meet the objectives of the mothers' outcomes. There were parallels between the nurses' and mothers' information on perceived barriers regarding their influence on implementing KC. The nineteen (19) items were modified, and this is shown in Table 3.4. Mothers were requested to circle a number to indicate important perceived barriers while implementing KC. A 5-point Likert response format was adopted. Descriptors were: not influential at all (1), not very influential (2), neither influential nor non-influential (3), somewhat influential (4), and very influential (5). With reference to the descriptors, the closer the score to 5, the higher the level of mothers' perceived barriers to KC implementation. Out of the nineteen (19) items, two (2) were negative statements, which were (16 & 17). Those items were rated reversely. A higher score indicated a higher level of perceived barriers with reference to the descriptors. The perceived barrier scores were transformed to mean scores, then classified into two (2) groups. A mean score of  $M=2.42$  and above indicated a high level of perceived barriers, and below  $M=2.42$  indicated a low level of perceived barriers to KC implementation.

***d) Part IV: Mother's Stress regarding Parental Stressor Scale: (PSS: NICU P&R)***

Part IV of the questionnaire refers to knowledge from mothers about stressful experiences when their preterm infant is admitted to the NICU. The scale, developed by Miles et al. (1999) in a validated questionnaire to measure parental perceptions of the stressors encountered in the NICU, puts emphasis on reactions to long stays in the NICU. The PSS: NICU:P&R has been used extensively all over the world. It has been used by researchers in Malaysia (Swee Long et al., 2017); India (Chourasia et al., 2013); Hong Kong (Liu et al., 2010); Norway (Kaarsen et al., 2006); USA (Melnyk et al., 2010; Melnyk et al., 2006; Turan et al., 2008); Australia (Sweet & Mannix, 2012); and Canada (Zelkowitz et al., 2008).

The PSS scores reported in the NICU validation test ranged from 0.70 to 0.98. Miles' latest revision is a self-report scale of 26 items that measure parental stress related to three NICU situations: NICU sight and sound (5 items), baby appearance, behavior, and treatments (14 items), and alteration of relationship and parental roles (7 items). The researchers in this study have used the Parental Stressor Scale: Neonatal Intensive Care Unit (PSS: NICU: P&R). Confirmatory factor analysis (CFA) to confirm the appropriateness of this instrument for the current setting, statistical methods performed to test the reliability of this question is to evaluate through Cronbach's alpha in this section was carried out on this part of the questionnaire (PSS: NICU: P&R). All seven (7) items were positively and negatively worded as shown in (Appendix B). Out of seven items, there were five positive statements, which were (1,3,4,5,7), and two negative statements, which were (2 and 6). A 5-point response Likert scale was used: not stressful at all (1), a little stressful (2), moderately stressful (3), very stressful (4), and extremely stressful (5). In the current study, PSS:NICU:P&R scores were categorized based on Chourasia et al., 2013, who rated level of stress as high-level stress (4-5), moderate level stress (3-3.99) and low stress (1-2.99). Scoring was presented as a mean score. For the purpose of KC-EP and kangaroo care implementation, maternal level of stress was further categorized. A higher score showed a higher stress level with reference to the descriptors; a high level was (3-5) and a low level was (1-2.99). The stress scores were calculated and converted into mean scores, then categorized into two (2) groups. The highest mean scores of  $M=2.63$  and below indicated a low level of stress while mean scores above  $M= 2.63$  indicated a high level of stress related to preterm infant's admission to NICU.

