## Part III: Perceived Barriers on KC

**Instruction:** Please indicate a very important perceived barrier of KC. Use the following scale for your responses:

5 = Very Influential

4 = Somewhat Influential

3 = Neither Influential Nor Non-Influential

2 = Not Very Influential

1 = Not Influential at All

No	Statement	5	4	3	2	1
1	Mothers' reluctance to allow KC.					
2	Mothers' belief that technology (e.g., incubators) is more beneficial to premature babies than care a mother can provide.					
3	Mothers' felt no privacy during KC.					
4	Mothers' difficult to assess baby's readiness for KC.					
5	Mothers' reluctance to initiate KC.					
6	Mothers' reluctance to participate in KC.					
7	Mothers' is frequently unavailable to do KC.					
8	Mothers' fear of safety for babies below a certain weight.					
9	Mothers' fear of low temperature during KC.					
10	Mothers' fear of baby's does not breastfeed during KC.					
11	Mothers' feel inability to provide adequate time to other children during KC.					
12	Mothers' belief that KMC is used for babies who are NOT developmentally well.					
13	Mothers' discomfort with exposing their chest during KC.					
14	Mothers' belief that will be much disturbance to the baby during KC.					
15	Mothers' unable to come to visit the baby for a long period of time.					
16	Mothers' felt nursing staff reluctance to participate in KC.					
17	Mothers' feel that KC adds a burden to nurses, inadequate time due to working commitment.					
18	Mothers' felt that KC makes it difficult to nurses to administer care.					
19	Mothers' felt the nursing staff's lack of exposure for mothers participating in KC.					

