#### Part IV: PARENTAL STRESS SCALE: NEONATAL INTENSIVE CARE UNIT

**Instruction:** On the questionnaire, circle the single number that best expresses how stressful each experience has been for you. The numbers indicate the following levels of stress:

5 = Extremely stressful

4 = Very stressful

3 = Moderately stressful

2 = A little stressful

1 = Not at all stressful the experience did not cause you to feel upset, tense, or anxious

No	Items	5	4	3	2	1
1.	Being separated from my baby	5	4	3	2	1
2.	Not feeding my baby myself	5	4	3	2	1
3.	Not being able to care for my baby myself (for example, diapering, bathing)	5	4	3	2	1
4.	Not being able to hold my baby when I want	5	4	3	2	1
5.	Feeling helpless and unable to protect my baby from pain and painful procedures	5	4	3	2	1
6.	Feeling helpless about how to help my baby during this time	5	4	3	2	1
7.	Not having time alone with my baby	5	4	3	2	1

\_\_\_\_\_ Thank you for your participating in this study \_\_\_\_\_

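### The scoring key reverses two of the 19 barrier items, and labels two of the seven stress items negative, although every printed item in both scales runs in the same direction

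*Combined protocol and SAP*

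**What the plan says.** **Barriers.** Section 3.8.1, Part III, gives 19 items scored from 1 (not influential) to 5 (very influential). A higher score means more perceived barriers, and a mean of 2.42 or more is classed as high. It then says that "two (2) were negative statements, which were (16 & 17). Those items were rated reversely". In Appendix E(a), Part III, item 16 is that mothers "felt nursing staff reluctance to participate in KC". Item 17 is that KC burdens nurses who are short of time. Item 18, which is not reversed, is that KC makes nurses' care harder to deliver.

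**Stress.** Section 3.8.1, Part IV, says of the seven items that "there were five positive statements, which were (1,3,4,5,7", and then lists "two negative statements, which were (2 and 6". It also says "A higher score showed a higher stress level with reference to the descriptors", and sets a cut-off at 2.63. Appendix E(a), Part IV, tells the mother to "circle the single number that best expresses how stressful each experience has been for you". Item 2 is "Not feeding my baby myself" and item 6 is "Feeling helpless about how to help my baby during this time". Part IV contains no sentence on reverse scoring.

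**Reliability.** Section 3.19.4 and Table 3.5 report pilot alphas of 0.873 for barriers and 0.951 for stress.

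**The concern.** Reversal is right only for an item worded against the direction of its scale, and neither form contains such an item. On the barrier form, staff reluctance and staff burden are obstacles like the other 17. Item 17 is reversed while item 18, of nearly the same content, is not. On the stress form, item 6 is labelled negative while item 5, also about feeling helpless, is labelled positive. The Malay forms in Appendix E(b) run the same way.

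For barriers the instruction is explicit, so an analyst who follows it subtracts two barriers that should be added. For stress the label invites the same treatment. Perceived barriers and stress are two of the four maternal outcomes in objective 1 (Section 1.5.2). They are measured at three time points, reported as mean scores (Table 3.4) and also split at the cut-offs.

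**Working it through.** The plan gives no figure for the effect of the key, so there is none to reproduce. The pilot alphas are the only published figures that bear on it.

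**Inputs.** Barriers: k = 19 items, m = 2 reversed, alpha 0.873, cut-off 2.42. Stress: k = 7, m = 2 if the negative items are reversed, alpha 0.951, cut-off 2.63. A reversed answer x becomes 6 − x.

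**Raw score for a mother who answers x to every item.** Score = ((k − m)x + m(6 − x))/k, with slope (k − 2m)/k.
- Barriers: slope 15/19 = 0.79. All 1s give (17 + 10)/19 = 1.42; all 5s give (85 + 2)/19 = 4.58.
- Stress, if reversed: slope 3/7 = 0.43. All 1s give (5 + 10)/7 = 2.14; all 5s give (25 + 2)/7 = 3.86.

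**Cut-offs as uniform answers.** x = (k × cut-off − 6m)/(k − 2m).
- Barriers: (45.98 − 12)/15 = 2.27 instead of 2.42.
- Stress, if reversed: (18.41 − 12)/3 = 2.14 instead of 2.63.

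**Illustration of misclassification (answers assumed).** Suppose a mother's other 17 barrier answers sum to 38. If she answers 5 to items 16 and 17, the unreversed mean is (38 + 10)/19 = 2.53, which is high. The key as written gives (38 + 2)/19 = 2.11, which is low. If she answers 1 to both, the two results swap.

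**Standardised effect, assuming unit-variance items with equal correlation r and a shift common to all items.** r = alpha/(k − (k − 1)alpha). The variance of the item sum is V = k + k(k − 1)r without reversal. With reversal it is V′ = k + 2r(S − D), where S and D count item pairs keyed in the same and in opposite directions. The standardised effect is multiplied by slope × √(V/V′).
- Barriers: r = 0.873/3.286 = 0.266; S = 137, D = 34; V = 109.9, V′ = 73.7. The ratio is 0.789 × √(109.9/73.7) = 0.964, a loss of about 4%.
- Stress, if reversed: r = 0.951/1.294 = 0.735; S = 11, D = 10; V = 37.9, V′ = 8.47. The ratio is 0.429 × √(37.9/8.47) = 0.906, a loss of about 9%.

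With 48 per group and an assumed standardised difference of 0.58, power falls from 81% to 78% for barriers and, if reversed, to 73% for stress.

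**Does the pilot alpha fit reversal?** Alpha after reversal = k/(k − 1) × (1 − k/V′).
- Stress: 7/6 × (1 − 7/8.47) = 0.20. Even at r = 1, V′ = 9 and alpha is 7/6 × (1 − 7/9) = 0.26. The reported 0.951 is therefore out of reach for same-direction, equally correlated items with two reversed.
- Barriers: 19/18 × (1 − 19/73.7) = 0.78. But 0.873 could also arise after reversal if r were about 0.44, so this alpha does not settle which key was used.

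**The case against.** The case against is strongest for stress. Part IV labels items 2 and 6 but never says they were reversed. The plan's usage is mixed. The barrier section and the nurses' perception and knowledge sections (Section 3.10.1, Parts I and II) say negative items were reversed. The mothers' knowledge and nurses' practice sections list negative items without saying so. The mothers' perception section lists reversed items without calling them negative. The pilot alpha also points to no reversal. All of this stands, so a reader who infers that stress was in fact scored with two items reversed goes further than the documents allow.

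Four further inferences about size are tempting but not supported:
- **That 1.42 to 4.58 and 2.14 to 3.86 are the possible score ranges.** They hold only for identical answers to every item; with mixed answers both scores can still run from 1 to 5.
- **That the 4-to-5 high-stress class becomes unreachable.** A mother answering 5 to six items and 4 to item 6 scores (25 + 1 + 2)/7 = 4.00.
- **That high scorers come out as average.** An all-5 mother scores 4.58 on barriers, well above 2.42, and 3.86 on stress, above both two-group cut-offs (3 and 2.63).
- **That the tested effects shrink to 79% and 43%.** Those are raw slopes. The standard deviation shrinks too, and the planned t-tests and general linear models depend on the ratio.

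The same key also applies to both groups, so the calculation shows attenuation and not a bias towards either group.

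What the objection does not remove is the barrier instruction, which is explicit and contradicts the printed items.

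**Conclusion.** The barrier key is wrong as written. Items 16 and 17 are scored against the direction the plan gives for the scale. The raw slope is 0.79 for uniform answers and the standardised loss about 4%. The more visible damage is to reported mean scores and to the high/low split at 2.42, where mothers can change class in either direction. The 4% rests on equal inter-item correlation and on a shift shared by all items. Items 16 and 17 concern nursing staff, who are themselves trained before the experimental group is recruited. If those two items move more than the rest, the loss would be larger.

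For stress, the label on items 2 and 6 is wrong, but the effect on scores is conditional. If reversal was applied, the raw slope is 0.43 and the standardised loss about 9%, and the written key is hard to square with an alpha of 0.951. If it was not, the defect is a mislabelled key that needs correcting. The point should be fixed; it does not threaten the design.

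**What to change.** In Section 3.8.1, state that all 19 barrier items and all seven stress items are scored 1 to 5 in one direction with no reversal, and delete the negative-item lists in Parts III and IV. Report which key produced the pilot alphas of 0.873 and 0.951. If any reversal was applied in the pilot or the main data, recompute the alphas and mean scores. Recompute the 2.42 and 2.63 cut-offs as well: the plan does not say how they were derived, so they may carry the same key.

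The cost is two passages of text and a few lines of scoring syntax run on the existing item-level answers. No new data are needed.

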### **3.9 Premature Infants**

The instrumentation for premature infants consisted of data from the KCPR or booklet provided. This comprised two sections; Section A for demographic characteristics and Section B for the data collection on preterm infant outcome variables at T0, T1, and T2. The KCPR booklet contained the following:

***a) Section A: Infant's Demographic Characteristics***

Section A collected the premature infants' demographic characteristics data from both groups. All nine (9) variables were formatted to gain information on the baseline data of the infants. The variables included gender, race, birth weight (kg), gestational age at birth (weeks), corrected age on recruitment (weeks), corrected age on discharge (weeks), mode of feeding (tube feed, syringe-feed, cup-feed or breastfeed), type of milk, expressed breast milk (EBM) or breastfeeding, initiation of breastfeeding (weeks) and weaning from breastfeeding (week/month). The rationale for using these variables was to assess if the selected variables had an impact in terms of primary and secondary outcomes on the perception, awareness, perceived barriers and stress of the mothers.

***b) Section B: Infant's Kangaroo Care Progress Record (KCPR) or Data Sheet***

Section B assessed the progress of the premature infant in terms of primary and secondary outcomes. The primary outcome variables were weight gain and LOS, while the secondary outcomes were breastfeeding rate or feeding status. All nine (9) items were adapted from the original article by Singh, Amritanshu and Mukherjee, (2014) and Biswas, Malpani & Ekka, (2016) with a slight modification and format to satisfy the research goals relevant to the main and secondary monitoring requirements of the use of KC to assess outcomes. The variables consisted of baseline temperature, age of KC initiation (week/days), weight at KC initiation (g/days), weight gain velocity (g/days), duration of KC (in hour/day), duration of stay (days), types of milk (EBM or breastfeeding), initiation of breastfeeding (weeks) and weaning from breastfeeding (weeks) for both groups. The KCPR booklet was designed and presented to the

respective control and experimental groups. The difference in the KCPR booklet was the knowledge needed for the experimental group to get the input given to the control group for preterm infants (routine activities and standard care) and KC performance. The data for the preterm infants in the control group were documented according to standard practice care or routine practice in the NICU. [Please refer to Appendix F(a) and F(b)].

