## **1.6 Hypothesis**

The following hypotheses guided the study:

- $H_1$ : A KC-EP can improve perception, knowledge, and perceived barriers in relation to KC, and levels of stress among mothers.
- $H_2$ : KC is effective in improving weight gain patterns, LOS, and breastfeeding rates among premature infants.
- $H_3$ : A KC-EP can improve nurses' perception, knowledge, and practice in relation to KC implementation.

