### 3.7.2 Sample Size Calculation for Mother-Infant Dyads

The sample size for mother-infant dyads was calculated using the two-sample independent t-test. This was based on a previous study and this study's primary outcome (Rao, Udani, & Nanavati, 2006). The two-tailed comparison group was used in the sample size calculation using the formula below. The mean difference in weight gain was 8.41 (Rao et. al., 2006) pre and post-intervention, while 0.8 was the standard deviation. These values were applied in the formula based on the study done by Rao et., al (2006).

$$\text{The formula, } n = \frac{2[Z\alpha/2 + Z\beta]^2 S^2}{(\mu_1 - \mu_2)^2}$$

$$\text{Thus, } Z\alpha/2 = 1.96 \quad Z\beta = 0.842$$

$$\mu_1 - \mu_2 = 0.54 \quad S = 0.8$$

$$\text{The formula, } n = \frac{2[1.96 + 0.84]^2 [0.8]^2}{(0.54)^2}$$

$$n = \frac{2 [ 2.802 ]^2 (0.64)}{0.29}$$

$$n = \frac{2 [ 7.85 ] (0.64)}{0.29}$$

$$n = \frac{10.05}{0.29}$$

Thus,  $n = 34.65 = 35$  subjects for each group.

Additional 30% = 50 subjects for each group.

An additional 30% was added to the estimated sample size to account for possible missing values and non- responses. The final sample size calculated was 50 for the sample population, and 50 for the experimental group.

The two groups of preterm infant-mothers were recruited from those who were admitted to the NICU. The first set of samples ( n=50) was recruited from early February 2018 until July 2018. The preterm infant-mother dyads who were admitted within these months were allocated to the control group, while recruitment for the experimental group of preterm infant-mother dyads (n=48) was initiated from early September 2018 until April 2019, after completion of the intervention program for the nurses. In both groups, the sample size for the control group was (n=48) and the experimental group (n=48), for a total sample size of (n=96).

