categorical variables are both independent and dependent variables. Therefore, covariance analysis was used to correct the observed effects on the outcome variables of potential confounders. The summary of the statistical analysis used for all research questions is outlined in Table 3.14. Each of the statistical tests is two-tailed. A p-value below 0.05 was assumed to show statistical significance.

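### Two primary infant outcomes are each tested at two-sided 0.05 with no order, adjustment or success rule, although only weight gain was sized

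*Combined protocol and SAP*

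**What the plan says.** - **Number of primaries.** Section 3.9 b), on the infant progress record, names two: "The primary outcome variables were weight gain and LOS, while the secondary outcomes were breastfeeding rate or feeding status".
- **Sizing.** Section 3.7.2 speaks of a single one: "This was based on a previous study and this study's primary outcome". The only effect it describes is on weight: "The mean difference in weight gain was 8.41". Neither LOS nor breastfeeding has a sample-size calculation.
- **Hypotheses.** Section 1.6 groups ten outcomes under three statements. H1 covers four maternal outcomes: "A KC-EP can improve perception, knowledge, and perceived barriers in relation to KC, and levels of stress among mothers". H2 covers three infant outcomes: "KC is effective in improving weight gain patterns, LOS, and breastfeeding rates among premature infants". H3 covers three nurse outcomes: "A KC-EP can improve nurses' perception, knowledge, and practice in relation to KC implementation".
- **Tests.** Table 3.4 gives weight gain, LOS and breastfeeding a row each, with separate tests. The maternal scores share one row and the nurse scores another. Section 3.19.1 then applies one criterion throughout: "Each of the statistical tests is two-tailed" and "A p-value below 0.05 was assumed to show statistical significance".
- **What is absent.** No section gives a testing order or a multiplicity adjustment, or says whether H1, H2 or H3 needs one significant outcome, the primaries, or all of them.

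**The concern.** Sections 3.7.2 and 3.9 b) disagree on how many primary outcomes there are. With two primaries each judged at 0.05, there are two chances of a chance finding, and three across H2. Because no success rule is fixed, the choice between counting any one outcome and requiring all of them could be made after the results are known. At stake is how far a statement that kangaroo care improves infant outcomes can be trusted if it rests on one significant result among several.

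**Working it through.** **The plan's own figure.** Inputs from section 3.7.2: Zα/2 = 1.96, Zβ = 0.842, difference 0.54, SD 0.8.

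n = 2 × (1.96 + 0.842)² × 0.8² / 0.54² = 34.45, rounded up to 35 per group. The plan shows 34.65 because it rounds intermediate values. Then 35 / (1 − 0.30) = 50 per group. The figure reproduces, and it covers one outcome tested at the full 0.05. The 8.41 in the text of that section is not the 0.54 in its formula. That is a separate matter, but it means the power figures below rest on the formula's inputs only.

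**False positives if any one result counts.** Assume no true effect on any outcome, one test per outcome, and each test holding its own 5% level.

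- Two primaries, independent: 1 − 0.95² = 9.75%. The bound without any assumption on dependence is 2 × 5% = 10%.
- Three H2 outcomes, independent: 1 − 0.95³ = 14.26%. The bound is 3 × 5% = 15%.
- Favourable direction only, at 2.5% per outcome: 1 − 0.975² = 4.94% and 1 − 0.975³ = 7.31%.

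Independence is doubtful. Sections 2.3.7 and 3.16.4 make weight a discharge criterion, so weight gain and LOS are linked. The documents give no correlation, so a range is assumed. Equally correlated normal test statistics were simulated (1,000,000 draws per setting), with each outcome oriented so that improvement is positive:

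| Assumed correlation | Two primaries, either direction | Three H2 outcomes, either direction | Two, favourable only | Three, favourable only |
|---|---|---|---|---|
| 0 (exact) | 9.75% | 14.3% | 4.9% | 7.3% |
| 0.5 | 9.0% | 12.5% | 4.5% | 6.3% |
| 0.8 | 7.8% | 9.8% | 3.9% | 4.9% |
| 0.9 | 7.0% | 8.4% | 3.5% | 4.2% |

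The nominal level is 5% for either direction and 2.5% for the favourable direction. Every entry exceeds its nominal level.

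**If H2 required all its outcomes.** A false claim then needs a significant result on at least one outcome with no true effect, and that has probability at most 5%. With no effect anywhere and independent tests it is 0.05² = 0.25% for two outcomes and 0.05³ = 0.01% for three.

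**Power for weight gain under a stricter level.** With 48 per group, 0.54 / (0.8 × √(2/48)) = 3.307.

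- At two-sided 0.05: Φ(3.307 − 1.960) = 91.1%.
- At two-sided 0.025: Φ(3.307 − 2.241) = 85.7%.

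**The case against.** The strongest reply is that no inflated error can be charged to H2 itself. Section 3.19.1 defines when a test is significant, not when a hypothesis is supported. H2 joins its outcomes with a conjunction, and read as requiring all of them its error stays within 5%. H2 also claims improvement, so only favourable results would support it, which halves the per-outcome rate. Weight gain and LOS are linked through the discharge criteria, which lowers the rate further. Finally, Table 3.4 already poses the three infant questions separately, so the infant analysis is less bundled than section 1.6 suggests.

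All of this limits the size, and all of it stands. It does not remove the gap. No section adopts the all-outcomes reading, and separate rows in Table 3.4 make it easy to claim a single significant outcome. Linked outcomes still leave the rate above nominal.

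Three stronger readings are tempting, and the documents do not support them.

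- *That the error for H2 simply is 10–14%.* This needs an any-one rule, independence and counting in either direction. The plan states neither of the first two, and H2 is worded as improvement.
- *That the trial carries a 40% error over its ten outcomes (1 − 0.95¹⁰).* These outcomes belong to three objectives, for mothers, infants and nurses, and no claim is defined as any one of the ten.
- *That LOS is the less supported primary.* The LOS literature section does report a randomised trial with 12.78 versus 12.86 days (p>0.93), and its weight gains of 23.99 and 15.58 g/day differ by the 8.41 used in section 3.7.2. The same section also reports shorter stays elsewhere (11.46 versus 17.68 days; 16.6 versus 20.7). The weight-gain section cites a randomised trial with no difference in weight gain. The documents do not rank the two.

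**Conclusion.** The concern holds in conditional form. Two primaries are named, one was sized, and each outcome is tested at two-sided 0.05 without order, adjustment or success rule. If any one significant result counts, the chance of at least one false positive is above 5%. It reaches about 10% for the two primaries and 14% for the three H2 outcomes under independence, and is about 7–9% and 8–12.5% at assumed correlations of 0.9 to 0.5. In the favourable direction only, it is up to about 5% and 7% against 2.5%. If all outcomes were required it would not exceed 5%.

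These figures assume one test per outcome. Section 3.16.4 records outcome weight at discharge, T1 and T2, and testing each time point separately would add to them. The same missing rule affects H1 and H3, but the plan does not call those outcomes primary.

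**What to change.** 1. Name one weight-gain measure and one time point. Section 3.9 b) lists a daily velocity, while Table 3.4 lists grams at T0, T1 and T2.
2. Choose one of two procedures and make sections 3.7.2, 3.9 b) and 3.19.1 agree with it.
   - *Ordered testing.* Test weight gain at 0.05, LOS at 0.05 only if weight gain is significant, and breastfeeding at 0.05 only if LOS is significant. Weight gain goes first because it is the outcome that was sized. This holds the error over the three infant outcomes at 5% whatever their correlation, and costs weight gain no power.
   - *Holm across both primaries.* Compare the smaller p-value with 0.025 and, if it passes, the larger with 0.05. Weight gain has about 86% power at 48 per group even at 0.025, on the formula inputs 0.54 and 0.8. Breastfeeding stays secondary.
3. State conclusions outcome by outcome rather than for H1, H2 or H3 as a whole. Holm within H1 (four scores) and within H3 (three scores) is optional.
4. Label the demographic association tests in section 3.19.1 as exploratory.
5. Sections 3.7.2 and 3.16 describe recruitment and data collection as already done. If data have been seen, report the choice of procedure, measure and time point as post hoc.

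The cost is analysis wording and a harder claim for LOS, which either waits on weight gain or may face the 0.025 level. No additional dyads are needed for weight gain on the formula's inputs.
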